13. TRIAL MEDICATION EXPOSURE

Exposure to trial medication will be presented at Primary Analysis for the SAF, at Final Analysis for the FAS, PPS and SAF.

The proportion of subjects treated at each planned visit (administration on Day 1, Day 8, and every other week until Day 162) and per treatment group will be presented.

Descriptive statistics for the number of injections from Day 1 up to Week 16 (included), from Week 16 (excluded) up to Week 24 and overall per subjects will be presented.

Number of subjects per duration of exposure categories, patient time (years) per duration of exposure categories, and descriptive statistics for duration of exposure will be presented.

Document: \\eedc-nas01a:\Boehringer_Ingelheim\BI_695501\XXA39605\Biostatistics\Documentation\SAP\15-v2.0\BI 1297.12 SAP v2.0 31JAN2018.docx

Author: Version Number: 2.0
Version Date: 31JAN2018

Template No: CS_TP_BS016 Revision 4
Effective Date: 01Apr2016

Reference: CS_WI_BS005

Exposure categories will be the following cumulative categories: ≥ 1 day, ≥ 2 weeks, ≥ 4 weeks, ≥ 12 weeks, ≥ 16 weeks, and ≥ 24 weeks.

13.1. DERIVATIONS

The date of first and last trial medication administration will be taken from the eCRF page “Trial Medication Injection”.

Duration of exposure (days) = (date of last injection - date of first injection + 1).

Duration of exposure (weeks) = Duration of exposure (days) / 7.

Patient Year Exposure (year) = cumulative duration of exposure in days per subjects / 365.25.

14. TRIAL MEDICATION COMPLIANCE

Compliance to trial medication will be presented at Primary Analysis for the SAF, at Final Analysis for the FAS, PPS and SAF.

14.1. DERIVATIONS

Compliance with trial medication will be based on the eCRF page “Trial Medication Injection”. An administered injection is considered when the question “Was full dose given” is answered “Yes”.

Compliance will be based on the comparison of actual administered injections and the planned usage. Compliance will include visits until treatment discontinuation.

- “Per visit” compliance will be calculated as follows and will correspond to the observed compliance between visit N and N-1:

Compliance (%) = (Number of administered injections at visit X) * 100 / Planned number of injections at visit X

Planned usage is detailed below.

- “Overall” compliance will be calculated as follows:

Compliance (%) = (Number of administered injections) * 100 / Planned number of injections

Where

Planned usage

Visit N	1	2	3	4	5	6	7	8	9
---------	---	---	---	---	---	---	---	---	---

Document: \\eedc-nas01a:\Boehringer_Ingelheim\BI_695501\XXA39605\Biostatistics\Documentation\SAP\15-v2.0\BI 1297.12 SAP v2.0 31JAN2018.docx

Author: Version Number: 2.0
Version Date: 31JAN2018

Template No: CS_TP_BS016 Revision 4
Effective Date: 01Apr2016

Reference: CS_WI_BS005

Number of injections between visit N and N-1	-	2	1	1	2	2	2	2	2
Planned cumulative number of injections	0	2	3	4	6	8	10	12	14

- “Week 16” compliance will be calculated considering the injections until Week 16 (visit 7) (included).

15. EFFICACY OUTCOMES

15.1. PRIMARY EFFICACY

15.1.1. PRIMARY EFFICACY VARIABLE & DERIVATION

The primary efficacy endpoint is:

- The proportion of subjects with at least 75% reduction in Psoriasis Area and Severity Index (PASI 75) response at Week 16

PASI reduction at Week 16 is assessed as the decrease relative to baseline measurement and expressed as a percentage:

- $\text{Reduction (\%)} = [100 * (\text{PASI at Baseline} - \text{PASI at Week 16}) / \text{PASI at Baseline}]$

In case of baseline value equal to 0 and non-missing post-baseline value recorded, then the change is set to 0% for the corresponding visit (no reduction).

Subjects with a reduction greater or equal to 75% are responders. Other subjects are considered as non-responders.

Document: \\ieedc-nas01a:\Boehringer_Ingelheim\BI_695501\XXA39605\Biostatistics\Documentation\SAP\15-v2.0\BI 1297.12 SAP v2.0 31JAN2018.docx

Author: Version Number: 2.0
Version Date: 31JAN2018

Template No: CS_TP_BS016 Revision 4
Effective Date: 01Apr2016

Reference: CS_WI_BS005

15.1.2. MISSING DATA METHODS FOR PRIMARY EFFICACY VARIABLE

15.1.2.1. Missing Data Methods for Primary Analysis: Non-Responder Imputation and Multiple Imputation

For the primary analysis, missing PASI 75 data will be imputed using a combination of non-responder imputation (NRI) and multiple imputation (MI) methods.

Unscheduled visits are in general not included in the analysis in this approach. However if an unscheduled visit was performed within a visit window. The visit closest to the planned visit date will be used for the analysis.

The following table details exactly where the NRI / MI imputation method will be applied for the primary analysis.

Table 1: Application of NRI / MI for the primary analysis on the FAS

Primary analysis (FAS)	prior to/on Week 16	
	Discontinued treatment [#]	Did NOT discontinue treatment
PASI 75 computable using observed data at Week 16	NRI	Observed
PASI 75 NOT computable using observed data at Week 16	NRI applied	MI applied

[#] lost to follow-up (according to eCRF record for “End of Treatment” or “Trial Completion”) is also included here, or patients who took a therapy that may significantly impact efficacy assessment prior to this time-point.

The following steps will be followed:

15.1.2.2. Multiple Imputation

STEP 1:

1. Creation of monotone missing data structure:

Intermediate (non-monotone) missing data will be multiple imputed using the Markov Chain Monte Carlo (MCMC) method and assuming MAR and multivariate Normality. The SAS procedure PROC MI with the MCMC option will be used.

The number of burn-in iterations has been identified based on approximately 90% of subject data up to Week 16 and fixed to 200.

This step will be performed on the longitudinal continuous PASI score (between Week 0 and Week 16), and SAS output for missing data pattern will be provided.

Baseline value will be imputed only if both Screening and Day 1 values are missing. Otherwise, the last available value will be considered as baseline value.

2. The datasets, now with monotone missing data, will be imputed further using sequential regression, with the following model for each visit:

Document: \\ieedc-nas01a:\Boehringer_Ingelheim\BI_695501\XXA39605\Biostatistics\Documentation\SAP\15-v2.0\BI 1297.12 SAP v2.0 31JAN2018.docx

Author: Version Number: 2.0
Version Date: 31JAN2018

Template No: CS_TP_BS016 Revision 4
Effective Date: 01Apr2016

Reference: CS_WI_BS005

PASI = Treatment + Prior exposure to a biological agent + <Previous baseline and Post-baseline data for the score>.

That is, if the screening visit is Visit 1 and PASI score S at Visit v is denoted S_v , then for example the model to impute PASI score S for Visit 4 will include observed S_1 and S_2 ; the model for Visit 5 will include observed S_1 , S_2 and S_4 .

This model includes fixed, categorical effects of:

- Treatment (BI 695501 versus US-sourced Humira)
- Prior exposure to a biologic agent (Yes versus No)

Note for 1 and 2: The seed 1000 will be used throughout. If a second seed is required, 1001 will be used, and so on as necessary.

The PASI 75 will then be calculated for each of the multiple imputed data sets.

15.1.2.3. Non Responder Imputation

STEP 2:

The imputed PASI 75 will be set to non-responder at Week 16 if the subject:

- discontinue treatment prior to Week 16
- or
- is lost-to-follow-up (according to eCRF record for “End of Treatment” or “Trial Completion”) prior to Week 16
- or
- has any severe violation related to any therapy that may significantly impact efficacy assessment prior to Week 16

Severe violation related to any therapy (according to CTP Table 4.2.2.1: 1) that may significantly impact efficacy assessment will be assessed by:

- providing to the trial medical advisor
- a list of medication codes (WHO Drug Dictionary version September 2016 or higher) presented in CTP Table 4.2.2.1: 1 and taken by at least one subject during trial conduct.
- full individual concomitant medication information including dose, frequency and Study day at start of medication.

Document: \\eedc-nas01a:\Boehringer_Ingelheim\BI_695501\XXA39605\Biostatistics\Documentation\SAP\15-v2.0\BI 1297.12 SAP v2.0 31JAN2018.docx

Author: Version Number: 2.0
Version Date: 31JAN2018

Template No: CS_TP_BS016 Revision 4
Effective Date: 01Apr2016

Reference: CS_WI_BS005

- Trial medical advisor will then identify the medications and start date of severe violation which may impact efficacy assessment

15.1.2.4. Missing Data Methods for Sensitivity Analysis: Non Responder Imputation and Last Observed Carried Forward

For the sensitivity analysis, missing PASI 75 data will be imputed using a combination of non-responder imputation and Last Observed Carried Forward (LOCF).

Only the data up to Week 16, inclusive, will be considered.

The following table details exactly where the NRI / LOCF imputation method will be applied for the sensitivity analysis.

Table 1: Application of LOCF / NRI for the primary analysis on the FAS

Primary analysis (FAS)	prior to/on Week 16	
	Discontinued treatment [#]	Did NOT discontinue treatment
PASI 75 computable using observed data at Week 16	NRI	Observed
PASI 75 NOT computable using observed data at Week 16	NRI applied	LOCF applied

[#] lost to follow-up (according to eCRF record for “End of Treatment” or “Trial Completion”) is also included here, or patients who took a therapy that may significantly impact efficacy assessment prior to this time-point.

The following steps will be followed:

a. Last Observed Carried Forward

STEP 1:

Missing PASI score will be imputed using LOCF method and PASI 75 will be calculated based on the imputed scores. Last observation will be carried forward as many times as needed.

b. Non Responder Imputation

STEP 2:

The imputed PASI 75 will be set to non-responder at Week 16 if the subject:

- discontinues treatment prior to Week 16
- are lost-to-follow-up (according to eCRF record for “End of Treatment” or “Trial Completion”) prior to Week 16
- have any severe violation related to any therapy that may significantly impact efficacy assessment prior to Week 16

Severe violation related to any therapy (according to CTP Table 4.2.2.1: 1) that may significantly impact efficacy

Document: \\ieedc-nas01a:\Boehringer_Ingelheim\BI_695501\XXA39605\Biostatistics\Documentation\SAP\15-v2.0\BI 1297.12 SAP v2.0 31JAN2018.docx

Author: Version Number: 2.0
Version Date: 31JAN2018

Template No: CS_TP_BS016 Revision 4
Effective Date: 01Apr2016

Reference: CS_WI_BS005

assessment will be assessed by:

- providing to the trial medical advisor
- a list of medication codes (WHO Drug Dictionary version September 2016 or higher) presented in CTP Table 4.2.2.1: 1 and taken by at least one subject during trial conduct.
- full individual concomitant medication information including dose, frequency, and Study day at start of medication.
 - Trial medical advisor will then identify the medications and start date of severe violation which may impact efficacy assessment

15.1.3. PRIMARY ANALYSIS OF PRIMARY EFFICACY VARIABLE

The primary efficacy analysis will be performed for the FAS.

The primary objective of this trial is to test the hypothesis that BI 695501 and US-sourced Humira are equivalent.

The test for equivalence will be performed with respect to BI 695501 versus US-sourced Humira.

The hypotheses for the equivalence test can be written as follows:

- H_0 : Difference in PASI 75 response rates at Week 16 (BI 695501 minus US-sourced Humira) is less than -18.0% or more than 18.0%
- H_1 : Difference in PASI 75 response rates at Week 16 (BI 695501 minus US-sourced Humira) is within [-18.0%, 18.0%]

To conclude equivalence, the two-sided 95% CI of the difference in PASI 75 response rate (BI 695501 – Humira) rounded to 1 decimal place has to be fully within the equivalence limits of $\pm 18.0\%$.

The primary analysis of the difference in PASI 75 response rates at Week 16 will be based on logistic regression with subsequent transformation of the estimated parameters to the difference in proportions.

The estimates from the logistic regression are on the logit scale, and the difference in proportions will be calculated as the difference between the predicted probabilities in the treatment groups on the original scale, with the variance calculated using the cumulative distribution function method of Reeve (Reeve 2016).

The statistical model can be described as follows:

(M1) $\text{Logit}(\text{response to treatment at Week 16}) = \text{Treatment} + \text{Baseline PASI} + \text{Prior exposure to a biologic agent} + \text{random error}$

This model includes fixed, categorical effects of:

- Treatment (BI 695501 versus US-sourced Humira)

Document: \\ieedc-nas01a:\Boehringer_Ingelheim\BI_695501\XXA39605\Biostatistics\Documentation\SAP\15-v2.0\BI 1297.12 SAP v2.0 31JAN2018.docx

Author:

Version Number:

2.0

Version Date:

31JAN2018

Template No: CS_TP_BS016 Revision 4
Effective Date: 01Apr2016

Reference: CS_WI_BS005

- Prior exposure to a biologic agent (Yes versus No)

and continuous effect of:

- Baseline PASI

The random error is assumed to be binomially distributed.

The analysis will consist of the following four steps:

STEP 1: Starting from the incomplete dataset, data imputation method are applied (described in section 15.1.2) to generate 1000 completed datasets.

STEP 2: Calculation of difference in proportion based on adjusted PASI 75 responders

The adjusted proportions of subjects with PASI 75 response in each groups at Week 16 are estimated from the logistics regressions on the logit scale, on each of the 1000 completed datasets.

The difference in proportions is calculated as the difference between the probabilities predicted by the model for both treatment groups on the original scale at Week 16.

STEP 3: Calculation of confidence intervals based on cumulative distribution function method of Reeve

The risk-difference confidence intervals are calculated on each completed datasets using the risk differences calculated in STEP 2) and the cumulative distribution function method of Reeve (Reeve 2016) with 1,000,000 simulations.

STEP 4: Computation of the final confidence interval

The estimated risk differences from STEP 2, and estimated standard errors back calculated using STEP 3 confidence intervals are combined using Rubin's Rules into the final confidence interval.

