7.2 NULL AND ALTERNATIVE HYPOTHESES

The test for equivalence will be performed with respect to BI 695501 versus US-sourced Humira.

The hypotheses for the equivalence test can be written as follows:

H_0 : Difference in PASI 75 response rates at Week 16 (BI 695501 versus US-sourced Humira) is less than -18% or more than 18%

H_1 : Difference in PASI 75 response rates at Week 16 (BI 695501 versus US-sourced Humira) is within $[-18\%, 18\%]$

To conclude equivalence, the two-sided 95% CI of the difference in PASI 75 response rate (BI 695501 – Humira) has to be fully within the equivalence limits of $\pm 18\%$.

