7.7 DETERMINATION OF SAMPLE SIZE

To perform the equivalence test BI 695501 versus US-licensed Humira with $\geq 85\%$ power, approximately 300 patients are needed for this comparison (FAS).

For the calculation of the sample size a meta-analysis on Week 16 data of the REVEAL and CHAMPION trials ([R14-4849](#), [R14-4898](#)) was performed. This meta-analysis revealed a risk difference of 64.2% and a 95% CI (60.4% to 67.9%). [Table 7.7: 1](#) shows the information used in the meta-analysis.

The classical 95-50-95 approach would give a non-conservative acceptance margin of 30.2% for the risk difference preserving 50% of the Humira effect.

Calculation of a conservative equivalence margin

Preserve 70% of the lower confidence limit (lcl) 60.4% (obtained from the meta-analysis) of the historical effect over placebo. Equivalence margin = $(1 - \text{preserved proportion}) * \text{lcl}$, $(1-0.7)*60.4\% = 18\%$.

Table 7.7: 1 CHAMPION and REVEAL results

Humira versus Placebo	Treatment			Placebo		
	Events	Total	%	Events	Total	%
CHAMPION	86	108	79.6%	10	53	18.9%
REVEAL	578	814	71%	26	398	7%

The weighted mean response rate is assumed to be the true response rate of 72%. This sample size is based on an assumed treatment difference in proportions of patients with PASI 75 at Week 16 of 0%, a standard proportion of 72% and an equivalence margin of 18%. At a power of 85% the sample size would be 288.

[Table 7.7: 2](#) presents the sample size at different margins and different power.

Table 7.7: 2 Sample size according to different scenarios

Assumed true response rate (RR)	Margin	Confidence level (two-sided)	Power	Sample Size [#] Equivalence
72%	15%	95%	75%	340
72%	15%	95%	80%	366
72%	15%	95%	85%	414
72%	15%	95%	90%	572
72%	18%	95%	75%	234
72%	18%	95%	80%	256
72%	18%	95%	85%	288
72%	18%	95%	90%	330
72%	20%	95%	75%	188
72%	20%	95%	80%	200
72%	20%	95%	85%	228
72%	20%	95%	90%	262

[#] Allocation ratio 1:1

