- The header should be placed at the top of the page (same place on each page) regardless of the size or orientation of the table or listing
- The customer name and protocol number should appear in row 1, left-aligned
- The output identification number should appear in row 2, left-aligned
- The output title should start in row 2 after output identification number separated by a double dot, left-aligned
- The output population should appear in row 2 after output title separated by a dash, left-aligned. The population should not be spelled out in full, e.g. FAS in preference to Full analysis set.
- Row 3 should be a continuous row of underscores ('_') (the number of underscores should equal the linesize)
- Row 4 should be a blank line
- Mixed case should be used for titles
- The output titles should be designed so that they are arranged consistently through all outputs. For example, content (e.g., Vital Signs) followed by metric (e.g., Change from Baseline) e.g. Vital Signs – Change from Baseline.
- Titles should not contain quotation marks or footnote references
- The column headings should be underlined with a row of underscores ('_')
- Column headings spanning more than one column should be underlined and have underscores on either side of the title and should be centered
- Column headings containing numbers should be centered
- Column headings should be in sentence case
- In general, the population count should appear in the column header in the form "(N=XXX)"
- "Statistic" should be the column header over n, Mean, SE, n (%) etc.
- As a rule, all columns should have column headings.

TABLE AND LISTING OUTPUT CONVENTIONS

General:

- The first row in the body of the table or listing should be blank
- The left hand column should start in column 1. No indenting or centering of the output should occur.

Document: \\ieedc-nas01a:\Boehringer_Ingelheim\BI_695501\XXA39605\Biostatistics\Documentation\SAP\15-v2.0\BI 1297.12 SAP v2.0 31JAN2018.docx

Author: Version Number: 2.0
Version Date: 31JAN2018

Template No: CS_TP_BS016 Revision 4
Effective Date: 01Apr2016

Reference: CS_WI_BS005

- Rounding should be done with the SAS function ROUND, if no further specification.
- Numbers in tables should be rounded, not truncated, if no further specification.
- Alphanumeric output should be left aligned.
- Numbers should be decimal point aligned.
- Whole numbers should be right aligned.
- Text values should be left aligned.

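### SAP 15.1.3 rounds the confidence limits to one decimal before comparing them with ±18.0%; Protocol 7.2 compares the unrounded interval, so the two rules differ in a narrow band at the margin

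*SAP*

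**What the plan says.** **Protocol, section 7.2.** The primary comparison uses a two-sided 95% interval for BI 695501 minus Humira. For equivalence to be concluded, that interval "has to be fully within the equivalence limits of" ±18%. The synopsis gives the same criterion. Neither place mentions rounding.

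**SAP, section 15.1.3.** The same sentence is repeated with an insertion: the interval "rounded to 1 decimal place has to be fully within the equivalence limits of" ±18.0%. The hypotheses stay at 18.0%. Under H1 the difference "is within [-18.0%, 18.0"%], a closed interval. No reason is given for the rounding.

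**SAP, Appendix 1.** The general output convention is: "Rounding should be done with the SAS function ROUND, if no further specification". The same appendix has percentages reported to one decimal place, so display rounding is already covered elsewhere.

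**Protocol, section 7.7.** The sample size takes the true difference between arms to be zero. It also rests on "a standard proportion of 72% and an equivalence margin of 18"%. The margin is derived as 30% of a lower confidence limit of 60.4%.

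**The concern.** In an equivalence trial the comparison of the confidence limits with the margin is the primary decision. Rounding for a table does no harm. Rounding before the comparison moves the point at which the decision changes. The SAP states its hypotheses at 18.0% but applies a rule that can accept an interval reaching slightly beyond 18.0%, so its decision rule does not quite match its own null hypothesis or the protocol's criterion.

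The practical stake is one narrow case. If a limit fell just beyond 18.00%, the SAP and the protocol would give opposite answers to the primary question, and a claim of equivalence resting on the rounding clause would be open to challenge. The wording also leaves unclear whether a rounded limit of exactly 18.0% passes.

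**Working it through.** **Inputs.** Response rate 72% in each arm, true difference 0, margin 18%, two-sided 95% CI, 1:1 allocation, power 85%, N = 288, about 300 randomized (Protocol 7.7). Rounding to one decimal and closed H1 (SAP 15.1.3). SAS ROUND, where a half rounds away from zero (SAP Appendix 1). The test rates of 54% and 90% are the two values 18 points from 72%.

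**1. Reproduce the protocol's sample size.** Two one-sided tests, unpooled normal approximation:

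n per arm = 2p(1-p)(z0.975 + z0.925)² / margin² = 2 × 0.72 × 0.28 × (1.960 + 1.440)² / 0.18² = 143.8

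This gives 144 per arm and N = 288, which matches. Some other cells of Table 7.7: 2 do not reproduce with this formula (for example 15% margin and 90% power: 572 stated, 466 computed). Nothing below depends on them.

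**2. Find the effective decision limit.**

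| Unrounded limit (absolute value) | Rounded | Protocol: at most 18% | SAP, rounded 18.0 passes | SAP, rounded 18.0 fails |
|---|---|---|---|---|
| 17.949% | 17.9 | pass | pass | pass |
| 17.95% | 18.0 | pass | pass | fail |
| 18.00% | 18.0 | pass | pass | fail |
| 18.04% | 18.0 | fail | pass | fail |
| 18.049% | 18.0 | fail | pass | fail |
| 18.05% | 18.1 | fail | fail | fail |

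On the closed reading the limit is just under 18.05%. On the strict reading it is just under 17.95%. The closed reading can only turn a protocol failure into a pass, because no limit at or inside 18.00% rounds past 18.0.

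**3. Type I error at the margin, 150 per arm, closed reading.** At a true difference of 18 points the per-side error is approximately Φ((limit - 0.18)/SE - 1.96).

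- Test 54%, reference 72%: SE = √(0.72 × 0.28/150 + 0.54 × 0.46/150) = 0.0548. Φ(-1.96 + 0.0005/0.0548) = 2.55%, against 2.50% without rounding.
- Test 90%, reference 72%: SE = √(0.72 × 0.28/150 + 0.90 × 0.10/150) = 0.0441. Φ(-1.96 + 0.0005/0.0441) = 2.57%, against 2.50%.

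Exact binomial enumeration of a Wald interval gives 2.40% to 2.45% (54% against 72%) and 2.67% to 2.74% (90% against 72%). The increase is 0.05 to 0.08 points in all four comparisons.

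**4. Power at zero difference, 150 per arm.** SE = √(2 × 0.72 × 0.28/150) = 0.0518, and power = 2Φ(limit/SE - 1.96) - 1. This is 86.9% at 18.00% and 87.2% at 18.05%, a change of about 0.2 points. The exact Wald enumeration moves from 87.1% to 87.5%. With 18.05% in the formula of step 1, N for 85% power is still 288.

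**5. Check against the margin's derivation.** (1 - 0.7) × 60.4% = 18.12%, stated as 18%. A limit of 18.05% preserves 1 - 18.05/60.4 = 70.1% of the historical lower limit; 18.00% preserves 70.2%.

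**The case against.** The best defence is that the rule is explicit, symmetric and written into the SAP. The protocol gives the margin as a whole percent, percentages are displayed to one decimal, and a written precision rule makes the decision agree with the table a reader sees. The Reeve interval is obtained by simulation, so a tolerance could also be defended as absorbing simulation noise. The derivation gives 18.12%, so the margin was itself rounded down by more than the disputed band.

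Part of this stands. The effect is close to nil, and the clinical justification of the margin is untouched. It does not make the two rules the same. Protocol 7.3.1 leaves details of the interval method to the analysis plan, whereas the decision criterion is set in 7.2 without rounding. The margin adopted is 18%; the spare 0.12 points was not adopted. The SAP does not give simulation noise as its reason, and with fixed seeds (1000 for imputation, 456 for the interval) the unrounded limit is reproducible.

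A reader might infer more than the documents support:

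- *That rounding pushes the type I error above its nominal level.* The step from 2.50% to 2.55% or 2.57% is asymptotic. In the exact Wald enumeration the error is below 2.5% with and without rounding in one scenario, and above it with and without rounding in the other. The approximation's own error (-0.10 to +0.17 points) exceeds the rounding effect. The 2.5% per side is also inferred from the two-sided 95% CI; the documents do not state it as an error rate.
- *That the primary decision has abandoned the stated margin.* The SAP keeps both hypotheses and the limits at 18.0%. What changes is the precision at which a limit is read, by at most 0.05 points.
- *That 18.05% is simply the new margin.* It depends on a rounded 18.0% counting as inside. Closed H1 makes that the natural reading, but the decision sentence does not define it.

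**Conclusion.** The discrepancy is real and minor. On the natural reading, a confidence limit between 18.00% and 18.05% in absolute value passes the SAP and fails the protocol. On the strict reading, a limit from 17.95% to 18.00% passes the protocol and fails the SAP. Outside these bands the rules agree.

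The operating-characteristic figures assume 150 per arm, 72% on reference and a Wald/normal interval. They do not describe the planned covariate-adjusted Reeve interval combined over imputations, for which the size of the effect was not computed. The 18.05% and 17.95% limits follow from the rounding rule alone and do not depend on that approximation. This is a wording alignment in the confirmatory rule, desirable but not essential. It does not bear on the effect estimate, the sample size or the margin's justification.

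**What to change.** Delete the rounding clause from the decision sentence in SAP 15.1.3. State that the unrounded lower and upper 95% confidence limits are compared with -18% and +18%, and that rounding applies to display only. Adding that a limit exactly equal to the margin counts as inside, in line with the closed H1, would remove the remaining ambiguity.

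The cost is one phrase. The sample size, model and interval code stay as they are. On the natural reading the rule becomes marginally stricter, by about 0.2 points of power at zero difference. If the analysis has already been run, reporting the unrounded limits against ±18% settles the matter.
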